Table 9 Management Guidelines for Dermatologic Events

Event	Management
Dermatologic event, Grade 1	
 • Continue atezolizumab. • Consider treatment with topical corticosteroids and/or other symptomatic therapy (e.g., antihistamines).
Dermatologic event, Grade 2	
 • Continue atezolizumab. • Consider patient referral to dermatologist. • Initiate treatment with topical corticosteroids. • Consider treatment with higher-potency topical corticosteroids if event does not improve.
Dermatologic event, Grade 3	
 • Withhold atezolizumab for up to 12 weeks after event onset. ^a • Refer patient to dermatologist. • Initiate treatment with 10 mg/day oral prednisone or equivalent, increasing dose to 1–2 mg/kg/day if event does not improve within 48–72 hours. • If event resolves to Grade 1 or better, resume atezolizumab. ^b • If event does not resolve to Grade 1 or better while withholding atezolizumab, permanently discontinue atezolizumab and contact Medical Monitor. ^c
Dermatologic event, Grade 4	
 • Permanently discontinue atezolizumab and contact Medical Monitor. ^c

^a Atezolizumab may be withheld for a longer period of time (i.e., >12 weeks after event onset) to allow for corticosteroids (if initiated) to be reduced to ≤10 mg/day oral prednisone or equivalent. The acceptable length of the extended period of time must be agreed upon by the investigator and the Medical Monitor.

^b If corticosteroids have been initiated, they must be tapered over ≥1 month to ≤10 mg/day oral prednisone or equivalent before atezolizumab can be resumed.

^c Resumption of atezolizumab may be considered in patients who are deriving benefit and have fully recovered from the immune-related event. Patients can be re-challenged with atezolizumab only after approval has been documented by both the investigator (or an appropriate delegate) and the Medical Monitor.

Appendix 9: Risks Associated with Atezolizumab and Guidelines for Management of Adverse Events Associated with Atezolizumab (cont.)

NEUROLOGIC DISORDERS

Myasthenia gravis and Guillain-Barré syndrome have been observed with single-agent atezolizumab. Patients may present with signs and symptoms of sensory and/or motor neuropathy. Diagnostic work-up is essential for an accurate characterization to differentiate between alternative etiologies. Management guidelines for neurologic disorders are provided in Table 10.

Table 10 Management Guidelines for Neurologic Disorders

Event	Management
Immune-related neuropathy, Grade 1	
 • Continue atezolizumab. • Investigate etiology.
Immune-related neuropathy, Grade 2	
 • Withhold atezolizumab for up to 12 weeks after event onset.^a • Investigate etiology. • Initiate treatment as per institutional guidelines. • If event resolves to Grade 1 or better, resume atezolizumab.^b • If event does not resolve to Grade 1 or better while withholding atezolizumab, permanently discontinue atezolizumab and contact Medical Monitor.^c
Immune-related neuropathy, Grade 3 or 4	
 • Permanently discontinue atezolizumab and contact Medical Monitor.^c • Initiate treatment as per institutional guidelines.
Myasthenia gravis and Guillain-Barré syndrome (any grade)	
 • Permanently discontinue atezolizumab and contact Medical Monitor.^c • Refer patient to neurologist. • Initiate treatment as per institutional guidelines. • Consider initiation of 1–2 mg/kg/day oral or IV prednisone or equivalent.

^a Atezolizumab may be withheld for a longer period of time (i.e., >12 weeks after event onset) to allow for corticosteroids (if initiated) to be reduced to ≤10 mg/day oral prednisone or equivalent. The acceptable length of the extended period of time must be agreed upon by the investigator and the Medical Monitor.

^b If corticosteroids have been initiated, they must be tapered over ≥1 month to ≤10 mg/day oral prednisone or equivalent before atezolizumab can be resumed.

^c Resumption of atezolizumab may be considered in patients who are deriving benefit and have fully recovered from the immune-related event. Patients can be re-challenged with atezolizumab only after approval has been documented by both the investigator (or an appropriate delegate) and the Medical Monitor.

Appendix 9: Risks Associated with Atezolizumab and Guidelines for Management of Adverse Events Associated with Atezolizumab (cont.)

IMMUNE-RELATED MENINGOENCEPHALITIS

Immune-related meningoencephalitis is an identified risk associated with the administration of atezolizumab. Immune-related meningoencephalitis should be suspected in any patient presenting with signs or symptoms suggestive of meningitis or encephalitis, including, but not limited to, headache, neck pain, confusion, seizure, motor or sensory dysfunction, and altered or depressed level of consciousness. Encephalopathy from metabolic or electrolyte imbalances needs to be distinguished from potential meningoencephalitis resulting from infection (bacterial, viral, or fungal) or progression of malignancy, or secondary to a paraneoplastic process.

All patients being considered for meningoencephalitis should be urgently evaluated with a CT scan and/or MRI scan of the brain to evaluate for metastasis, inflammation, or edema. If deemed safe by the treating physician, a lumbar puncture should be performed and a neurologist should be consulted.

Patients with signs and symptoms of meningoencephalitis, in the absence of an identified alternate etiology, should be treated according to the guidelines in [Table 11](#).

Table 11 Management Guidelines for Immune-Related Meningoencephalitis

Event	Management
Immune-related meningoencephalitis, all grades	
 • Permanently discontinue atezolizumab and contact Medical Monitor.^a • Refer patient to neurologist. • Initiate treatment with 1–2 mg/kg/day IV methylprednisolone or equivalent and convert to 1–2 mg/kg/day oral prednisone or equivalent upon improvement. • If event does not improve within 48 hours after initiating corticosteroids, consider adding an immunosuppressive agent. • If event resolves to Grade 1 or better, taper corticosteroids over ≥1 month.

^a Resumption of atezolizumab may be considered in patients who are deriving benefit and have fully recovered from the immune-related event. Patients can be re-challenged with atezolizumab only after approval has been documented by both the investigator (or an appropriate delegate) and the Medical Monitor.

Official Title: A Phase III, Open-Label, Multicenter, Three-Arm, Randomized Study to Investigate the Efficacy and Safety of Cobimetinib Plus Atezolizumab and Atezolizumab Monotherapy vs. Regorafenib in Patients With Previously Treated Unresectable Locally Advanced or Metastatic Colorectal Adenocarcinoma

NCT Number: NCT02788279

Document Date: SAP Version 2: 27-Nov-2017

STATISTICAL ANALYSIS PLAN

TITLE: A PHASE III, OPEN-LABEL, MULTICENTER, THREE-ARM, RANDOMIZED STUDY TO INVESTIGATE THE EFFICACY AND SAFETY OF COBIMETINIB PLUS ATEZOLIZUMAB AND ATEZOLIZUMAB MONOTHERAPY VS. REGORAFENIB IN PATIENTS WITH PREVIOUSLY TREATED UNRESECTABLE LOCALLY ADVANCED OR METASTATIC COLORECTAL ADENOCARCINOMA

PROTOCOL NUMBER: GO30182

STUDY DRUG: Cobimetinib; atezolizumab

VERSION NUMBER: 2

IND NUMBER: 130,091

EUDRACT NUMBER: 2016-000202-11

SPONSOR: F. Hoffmann-La Roche Ltd

PLAN PREPARED BY: [REDACTED], Ph.D

DATE FINAL: 02 March 2017

DATE AMENDED: Version 2: See electronic date stamp below

STATISTICAL ANALYSIS PLAN APPROVAL

Name	Reason for Signing	Date and Time (UTC)
[REDACTED]	Company Signatory	27-Nov-2017 21:56:09

CONFIDENTIAL

This is an F. Hoffmann-La Roche Ltd document that contains confidential information. Nothing herein is to be disclosed without written consent from F. Hoffmann-La Roche Ltd.

STATISTICAL ANALYSIS PLAN AMENDMENT RATIONALE for Version 2

The Statistical Analysis Plan (SAP) has been amended mainly due to the change in the order of hierarchical testing for efficacy endpoints, overall survival (OS), progression-free survival (PFS) and objective response rate (ORR).

GO30182 was designed and powered to evaluate the primary endpoint, OS in two comparisons: Arm A (cobimetinib plus atezolizumab) versus Arm C (regorafenib), and Arm B (atezolizumab) versus Arm C.

However, the original procedure to control type 1 error proposed in the SAP Version 1 (v1) consisted of OS as well as two secondary endpoints, PFS and ORR, in the hierarchical testing order of: OS, PFS and ORR in the comparison of Arm A vs. Arm C, followed by OS, PFS and ORR in the comparison of Arm B vs. Arm C.

Therefore, in order to adequately test the primary endpoint (OS) in both comparisons, while maintaining appropriate type 1 error control, the SAP is revised to keep only the primary comparisons in the hierarchical testing procedure (OS in Arm A versus Arm C, followed by OS in Arm B versus Arm C). Analysis of all secondary endpoints including PFS and ORR will be performed and will be submitted to health authorities according to the methodologies stated in the protocol and SAP.

TABLE OF CONTENTS

1.	BACKGROUND	6
2.	STUDY DESIGN	6
2.1	Protocol Synopsis	8
2.2	Outcome Measures	8
2.2.1	Primary Efficacy Endpoint.....	8
2.2.2	Secondary Efficacy Endpoints	8
2.2.3	Exploratory Analyses Endpoints	8
2.2.4	Patient-Reported Outcomes Objectives.....	9
2.2.5	Pharmacokinetic Efficacy Outcome Measures	9
2.2.6	Safety Outcome Measures	9
2.3	Determination of Sample Size	10
2.4	Analysis Timing	11
2.4.1	Primary Analysis Timing	11
2.4.2	Analysis Timing for Experimental Arm Comparison	11
3.	STUDY CONDUCT	12
3.1	Randomization Issues	12
3.2	Data Monitoring	12
4.	STATISTICAL METHODS	12
4.1	Analysis Populations	12
4.1.1	Efficacy Analysis Population.....	12
4.1.2	Pharmacokinetic-Evaluable Population	12
4.1.3	Safety Population	13
4.2	Analysis of Study Conduct.....	13
4.3	Analysis of Treatment Group Comparability	13
4.4	Efficacy Analysis.....	13
4.4.1	Primary Efficacy Endpoint.....	13
4.4.2	Secondary Efficacy Endpoints.....	14
4.4.2.1	Progression-Free Survival	14
4.4.2.2	Objective Response Rate.....	14
4.4.2.3	Duration of Response	15

4.4.2.4	Patient-Reported Outcomes	15
4.4.3	Exploratory Efficacy Endpoints	16
4.4.3.1	Overall Survival/Progression-Free Survival Rate at Fixed Timepoints	16
4.4.3.2	Time to Response	16
4.4.3.3	Health Economic Analyses	16
4.4.4	Evaluation of Each Drug's Contribution to The Combination	17
4.4.5	Sensitivity Analyses	17
4.4.5.1	Loss to Follow-Up for Overall Survival Analyses	17
4.4.5.2	Missing Tumor Assessment.....	17
4.4.6	Subgroup Analyses	17
4.5	Pharmacokinetic and Pharmacodynamic Analyses	18
4.6	Safety Analyses	19
4.6.1	Exposure of Study Medication	19
4.6.2	Adverse Events	19
4.6.3	Laboratory Data	19
4.6.4	Vital Signs.....	20
4.7	Immunogenicity Analyses	20
4.8	Missing Data	20
4.9	Exploratory analyses	20
5.	REFERENCES	21

LIST OF TABLES

Table 1	Analysis for Overall Survival for Primary Comparisons (Arm A vs. Arm C and Arm B vs. Arm C)	11
Table 2	Operating Characteristics for the Comparison of Arm A versus Arm B with Approximately 165 Overall Survival Events	12

LIST OF FIGURES

Figure 1	Study Schema.....	7
Figure 2	Overview of Hierarchical Testing Sequence for Type 1 Error a Control (2-Sided).....	10

LIST OF APPENDICES

Appendix 1	Protocol Synopsis	22
Appendix 2	Schedule of Assessments.....	33
Appendix 3	Schedule of Pharmacokinetic and Immunogenicity Samples.....	44
Appendix 4	Internal Monitoring Committee Charter	45

1. **BACKGROUND**

This Statistical Analysis Plan (SAP) provides details of the planned analyses and statistical methods for Study GO30182 (IMblaze370): A Phase III, open-label, multicenter, three-arm, randomized study to investigate the efficacy and safety of cobimetinib plus atezolizumab and atezolizumab monotherapy versus regorafenib in patients with previously treated unresectable locally advanced or metastatic colorectal adenocarcinoma. The background for the study can be found in the study protocol.

It is anticipated that positive results from Study GO30182 will support the submission of filing applications globally for the use of cobimetinib plus atezolizumab for the treatment of patients with chemotherapy-refractory, unresectable, locally advanced or metastatic colorectal cancer. For purposes of registration, the analyses outlined in this SAP will supersede those specified in the protocol.

2. **STUDY DESIGN**

This is a Phase III, multicenter, open-label, three-arm, randomized study in patients with unresectable locally advanced or metastatic colorectal cancer (mCRC) who have received at least two prior regimens of cytotoxic chemotherapy for metastatic disease. The study compares regorafenib, a standard-of-care therapy in this setting, with cobimetinib plus atezolizumab and atezolizumab monotherapy.

[figure not shown]
This study will be conducted globally, and approximately 360 patients will be randomized in a 2:1:1 ratio to one of the following treatments:

- Arm A: cobimetinib 60 mg orally on Days 1–21 plus atezolizumab 840 mg intravenous (IV) on Day 1 and Day 15 in a 28-day cycle (n=approximately 180), or
- Arm B: atezolizumab monotherapy 1200 mg IV on Day 1 in a 21-day cycle (n=approximately 90), or
- Arm C: regorafenib 160 mg orally on Days 1–21 in a 28-day cycle (n=approximately 90).

Stratification factors are extended RAS mutation status of the tumor and time since diagnosis of first metastasis (< 18 months vs. ≥ 18 months). Permuted-block randomization will be applied to ensure a balanced assignment to each treatment arm. Randomization and stratification will be managed through an interactive voice/web response system (IxRS).

At least 50% of patients with extended RAS-mutant tumors (refer to Protocol Section 4.5.7.1 for definition) will be enrolled in each arm. Enrollment of patients with microsatellite (MSI)-high status (see Protocol Section 4.5.7.1 for definition) will be limited to approximately 5% to reflect the natural prevalence in mCRC ([Goldstein et al. 2014](#)). [Figure 1](#) illustrates the study schema.

Figure 1 Study Schema

Stratified by tumor extended RAS status and time since diagnosis of first metastasis
MSI-H capped at approximately 5%
At least 180 patients with extended RAS-mutant tumors to be enrolled

mCRC=metastatic colorectal cancer; MSI-H=microsatellite high.

Patients will undergo tumor assessments at baseline and every 8 weeks (± 7 days), regardless of any dose delays or treatment cycle, until documented investigator-determined progressive disease, loss of clinical benefit, withdrawal of consent, death, or study termination by the Sponsor, whichever occurs first. Tumor response will be evaluated according to Response Evaluation Criteria in Solid Tumors Version 1.1 (RECIST v1.1). Any evaluable and measurable disease must be documented at screening and re-assessed at each subsequent tumor evaluation.

Treatment will continue until the patient has disease progression according to RECIST v1.1, unacceptable toxicity, death, patient or physician decision to withdraw, or pregnancy, whichever occurs first. Patients in all treatment arms are allowed to receive study treatment beyond disease progression if certain conditions are met (see Protocol Section 4.3.2.4).

After completion of study treatment, patients may receive any subsequent line of therapy as directed by their treating physician.

Patients who discontinue treatment for reasons other than disease progression (e.g., toxicity) will continue scheduled tumor assessments until disease progression, withdrawal of consent, study termination by Sponsor, or death, whichever occurs first. In the absence of disease progression, tumor assessments should continue regardless of whether patients start a new anti-cancer therapy, unless consent is withdrawn. All patients will be followed for survival unless consent is withdrawn.

The primary efficacy endpoint is overall survival (OS), which is defined as the time (in months) between the date of randomization and the date of death due to any cause. Patients who have not died at the time of analysis will be censored at the date when they were last known to be alive.

The analysis of the primary endpoint of OS will occur after a total of approximately 235 deaths have occurred.

The secondary endpoints include investigator-assessed progression-free survival (PFS), objective response rate (ORR), and duration of response (DOR) per RECIST v1.1. The analyses of PFS, ORR, and DOR will take place at the time of final analysis of OS.

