- The protocol has been amended to reflect the update to the Statistical Analysis Plan (SAP). Overall survival (OS) will remain the primary endpoint. However, the hierarchical testing procedure will only include the OS comparisons between arms. The secondary endpoints (progression-free survival [PFS] and objective response rate [ORR]) will be deleted from the testing hierarchy and analyzed based on the methodologies stated in the revised SAP. The rationale for this amendment is to test the primary endpoint (OS) in both comparisons, (Arm A versus Arm C and Arm B versus Arm C) while maintaining type-1 error (Section 6.1, Figure 3). The time of analysis has been updated accordingly and will be conducted when there are approximately 235 deaths in the study, which is expected to occur 23 months after the first patient is randomized (Sections 3.2 and 6.1).
- References to Foundation Medicine have been removed from Section 4.5.7.1 because Foundation Medicine is no longer being used for centralized confirmation of RAS and microsatellite testing.
- References to guidelines for managing cobimetinib-specific adverse events have been updated (Sections 5.1.1.1, 5.1.1.2, and 5.1.1.3).
- The reporting of adverse events after initiation of study drug has been updated to align with the Schedule of Assessments and to align with current model document language (Section 5.3.1).
- The reporting of the term “sudden death” has been updated to also require the presumed cause of death (Section 5.3.5.8).
- Event reporting for hospitalization has been clarified (Section 5.3.5.11).
- Contact information regarding Medical Monitors has been updated (Section 5.4.1).
- Language has been added to clarify that the end of the adverse event reporting is defined as 90 days after the last dose of study drug or initiation of a new anti-cancer treatment, whichever comes first (Sections 5.4.2.2 and 5.6).
- The reference document for assessing the expectedness of adverse events for regorafenib has been updated from local prescribing information to Summary of Product Characteristics (Section 5.7).
- The process for reviewing and handling protocol deviations has been updated per internal standard operating procedures (Section 9.2).
- The web address for the Roche Global Policy on Sharing of Clinical Trials Data (Section 9.5).

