6.4.2 Secondary Efficacy Endpoints

The secondary endpoints include investigator-assessed PFS, ORR, and DOR per RECIST v1.1. The analyses of PFS, ORR, and DOR will take place at the time of the OS analysis.

PFS is defined as the time between date of randomization and the date of first documented disease progression or death, whichever occurs first. Disease progression will be determined based on investigator assessment using RECIST v1.1. Data from patients who have not experienced disease progression or death will be censored at the last tumor assessment date and known to be free of disease progression. Data from patients with no post-baseline tumor assessment will be censored at the randomization date plus 1 day. Comparisons with respect to PFS between the two treatment arms will be tested based on a 2-sided stratified log-rank test. The HR for PFS will be estimated using a stratified Cox model. Two-sided 95% CIs for the HR will be provided. Stratified analyses will incorporate the same stratification factors as for the analysis of OS.

Results from an unstratified log-rank test and the unstratified HR will also be presented. Kaplan-Meier methodology will be used to estimate median PFS for each treatment arm, and the Kaplan-Meier curves will be provided.

ORR is defined as the proportion of patients who had a confirmed objective response of CR or PR assessed by the investigator according to the RECIST v1.1. An estimate of ORR and its 95% CI will be calculated using the Clopper-Pearson method for each treatment arm.

Treatment difference in ORR will be tested using the stratified Cochrane-Mantel-Haenszel test, stratified by the same factors used in the OS analysis, and a 95% Hauck-Anderson CI will be calculated for the difference in ORR between treatment arms.

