2.3 DETERMINATION OF SAMPLE SIZE

The study will randomize approximately 360 patients, including a minimum of 180 patients with extended RAS-mutant mCRC (assuming a prevalence of at least 50%), to cobimetinib plus atezolizumab (Arm A), atezolizumab monotherapy (Arm B), and regorafenib (Arm C) with the randomization ratio of 2:1:1, respectively.

The type 1 error (α) for the analysis of the primary endpoint of OS in the comparison of Arm A versus Arm C (the control arm) is 0.05 (2-sided). If OS is statistically significant in the comparison of Arm A versus Arm C, then the OS comparison of Arm B versus Arm C will be tested at a 2-sided α -level of 0.05.

The overview of the type 1 error (α) control is shown in [Figure 2](#).

Figure 2 Overview of Hierarchical Testing Sequence for Type 1 Error^a Control (2-Sided)

OS=overall survival

^a OS will be tested at a 2-sided significance level $\alpha=0.05$ only if the result of previous testing is positive (i.e., statistically significant).

The sample size of this study is determined on the basis of the number of events required to demonstrate efficacy with regard to OS in both comparisons (Arm A vs. Arm C and Arm B vs. Arm C).

The estimate of the number of events required to demonstrate efficacy with regard to OS is based on the following assumptions:

- Two-sided significance level of 0.05
- Arm A versus Arm C: 87% power to detect an hazard ratio (HR) of 0.61, corresponding to an improvement in median OS from 6.4 months in Arm C to 10.5 months in Arm A
- Arm B versus Arm C: 80% power to detect an HR of 0.61, corresponding to an improvement in median OS from 6.4 months in Arm C to 10.5 months in Arm B
- No interim analysis for OS

- Dropout rate of 10% in 24 months
- Hierarchical testing of Arm A versus Arm C followed by Arm B versus Arm C to control the overall α level of 5%

With these assumptions, approximately 360 patients in total will be randomized into this study, with approximately 270 patients for the comparison of Arm A versus Arm C and approximately 180 patients for the comparison of Arm B versus Arm C. The OS final analysis will be conducted when there are approximately 235 deaths occurring from all three arms. At this time, it is expected that approximately 178 deaths for the comparison of Arm A versus Arm C and approximately 127 deaths for the comparison of Arm B versus Arm C will have occurred.

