4.4.2 Secondary Efficacy Endpoints

4.4.2.1 Progression-Free Survival

PFS is defined as the time between the date of randomization and the date of first documented disease progression or death, whichever occurs first. Disease progression will be determined on the basis of investigator assessment using RECIST v1.1. Data for patients who are alive and have not experienced disease progression at the time of analysis will be censored at the date of last tumor assessment. Data from patients with no post-baseline tumor assessment will be censored at the randomization date plus 1 day. PFS will be analyzed using the same methods as described in Section 4.4.1.

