4.4.2.2 Objective Response Rate

ORR is defined as the proportion of patients who had a confirmed objective response of CR or PR assessed by the investigator according to the RECIST v1.1. The analysis population for ORR will be all randomized patients with measurable disease at baseline (i.e., patients with at least one measurable lesion according to RECIST v1.1 based on investigator assessment). An estimate of ORR and its 95% CI will be calculated using the Clopper-Pearson method for each treatment arm.

Treatment difference in ORR will be tested using the stratified Cochrane-Mantel-Haenszel test, stratified by the same factors used in the OS analysis, and a 95% Hauck-Anderson CI will be calculated for the difference in ORR between treatment arms.

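### PFS and ORR could follow the two OS tests in the fixed sequence at no cost to OS; as written they are tested with no alpha, gate or descriptive label

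*SAP*

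**What the plan says.** The SAP's amendment rationale reports that the Version 1 order was "OS, PFS and ORR in the comparison of Arm A vs. Arm C, followed by OS, PFS and ORR in the comparison of Arm B" versus Arm C. OS for B versus C therefore came fourth, behind two secondary endpoints. In Version 2, "the SAP is revised to keep only the primary comparisons in the hierarchical testing procedure". The stated purpose is to test OS adequately in both comparisons with type 1 error controlled. The protocol's amendment rationale agrees: "The secondary endpoints (progression-free survival [PFS] and objective response rate [ORR]) will be deleted from the testing hierarchy".

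The current body text matches. SAP Section 2.3 and protocol Section 6.1 give two-sided 0.05 to OS for A versus C; if that is significant, "then the OS comparison of Arm B versus Arm C will be tested at a 2-sided α -level of 0.05". Nothing follows in the sequence.

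PFS and ORR are nevertheless tested:

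- **PFS.** SAP Section 4.4.2.1: "PFS will be analyzed using the same methods as described in Section 4.4.1". Protocol Section 6.4.2: "Comparisons with respect to PFS between the two treatment arms will be tested based on a 2-sided stratified log-rank test".
- **ORR.** SAP Section 4.4.2.2: "Treatment difference in ORR will be tested using the stratified Cochrane-Mantel-Haenszel test".

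The amendment rationale adds that the secondary results will go to health authorities.

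**The concern.** The difficulty with the Version 1 order was that OS for B versus C could be reached only through PFS and ORR for A versus C. Moving those endpoints behind both OS tests removes the difficulty as completely as deleting them does, because in a fixed sequence a later test cannot affect an earlier one. Neither document says why deletion was preferred.

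The text also leaves the status of the PFS and ORR p-values open. SAP Section 4.4.2.1 sends PFS to Section 4.4.1, which takes its level from Section 2.3, and Section 2.3 gives a level only to OS. Elsewhere the plan says so when an analysis is not confirmatory: SAP Section 4.4.2.3 rules out formal testing for duration of response, Section 4.4.3.2 does the same for time to response, and protocol Section 6.4.1 calls A versus B descriptive. PFS and ORR carry no such statement.

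Two things are at stake: the chance to make a controlled PFS or ORR claim after a positive OS result, and the risk that an uncontrolled p-value below 0.05 is read as one.

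**Working it through.** **Inputs.** From SAP Sections 2.3 and 2.4.1: 178 deaths for A versus C, 127 for B versus C, 235 in total, HR 0.61 for both, 2:1:1 allocation, two-sided 0.05. The correlation among OS, PFS and ORR is not in the documents; it is assumed and varied over 0, 0.3, 0.6 and 0.9.

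**1. The plan's own power figures.** With Schoenfeld's approximation the log-rank statistic has mean √(d·p·(1−p))·|ln HR|.

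- A versus C: √(178 × 2/3 × 1/3) × 0.494 = 3.11; power Φ(3.11 − 1.96) = 87.5% (stated 87%).
- B versus C: √(127 × 1/4) × 0.494 = 2.79; power Φ(2.79 − 1.96) = 79.5% (stated 80%).
- Minimum detectable HR, exp(−1.96/√(d·p·(1−p))): 0.732 and 0.706 (stated 0.73 and 0.71).

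The planning figures reproduce.

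**2. Four uncontrolled 5% tests (PFS and ORR, two comparisons), all nulls true.** If independent, 1 − 0.95⁴ = 18.5%. They are not independent. Sharing Arm C under 2:1:1 gives a correlation between the two comparisons of 1/√(1.5 × 2) = 0.577. Multivariate-normal simulation (1,000,000 runs per setting) gives:

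| Assumed endpoint correlation | At least one false positive |
|---|---|
| 0 | 16.9% |
| 0.3 | 16.5% |
| 0.6 | 15.2% |
| 0.9 | 12.2% |

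**3. Six-step sequence.** The order is OS A–C, OS B–C, PFS A–C, ORR A–C, PFS B–C, ORR B–C, each at 0.05 and gated on all earlier tests. The first true null in the order must be rejected at 0.05 before any other false rejection can occur, so family-wise error cannot exceed 5%. Simulation agrees, within simulation error: 5.0% under the global null, 5.0% when the OS effects are very large and the secondary nulls are true, and 2.5 to 3.7% at the OS design alternative with the secondary nulls true. The probability of winning OS is the same with and without the added steps: 87.5% for A versus C, and about 74% for B versus C through the gate.

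**4. How often the added steps are reached.** Deaths per arm follow from the totals: C = 178 + 127 − 235 = 70, A = 178 − 70 = 108, B = 127 − 70 = 57. The correlation from these counts is (1/70)/√[(1/108 + 1/70)(1/57 + 1/70)] = 0.52. The bivariate-normal probability of winning both OS tests at HR 0.61 is 0.734 with this correlation and 0.740 with 0.577. Holding A versus C at 0.61, using correlation 0.52, and varying B versus C over assumed values:

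| HR, B versus C | Both OS tests significant |
|---|---|
| 0.61 | 73% |
| 0.70 | 50% |
| 0.80 | 24% |
| 0.90 | 9% |

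**The case against.** Confining confirmatory claims to OS is a legitimate choice, and it was openly disclosed. PFS and ORR are investigator-assessed in an open-label trial, and neither document plans a claim on them. The documented aim is fully met by the two OS tests. All of this stands. A reader might infer that the deletion damaged the trial's type 1 error control, or that uncontrolled secondary tests are an error in themselves; neither follows. OS control is correct, and uncontrolled secondary analyses are permissible when labelled descriptive. What is missing is the label, and an error-controlled route to a claim that would have cost nothing.

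The size can also be overstated. The 18.5% ignores the shared control arm and the correlation of PFS with ORR. Counting the two patient-reported scales in both comparisons would give 1 − 0.95⁸ = 34%, but that again assumes independence. The SAP says only that those scales are compared among treatment groups, they were not in the Version 1 hierarchy, and the change proposed here leaves them as they are.

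The strongest practical objection concerns the order. SAP Section 1 anticipates filing for the combination, and Section 4.4.4 plans for A versus C succeeding on OS while B versus C does not. In that case the six-step sequence stops and the combination's PFS and ORR stay nominal, whereas Version 1 would have reached them straight after OS for A versus C. Nor can one infer that the added tests would usually be reached: that needs HR 0.61 for atezolizumab alone, while protocol Section 1.6 reports disappointing checkpoint-inhibitor results in this setting and MSI-high enrolment is capped near 5%. These limits stand. Against the current plan, however, the added steps can only add claims.

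**Conclusion.** This is a small, free improvement confined to the secondary endpoints. The OS tests, their alpha and their power need no correction. As written, no PFS or ORR result can support an error-controlled claim even when both OS tests succeed, and the text does not say that their p-values are descriptive. The 12 to 17% false-positive figure matters only if those p-values are read as claims; it rests on a multivariate-normal approximation and assumed endpoint correlations. The benefit of appending the tests depends on OS for B versus C also succeeding, and the probability of that falls quickly as its hazard ratio moves away from 0.61. When it fails, PFS and ORR remain nominal, as they are now.

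**What to change.** In SAP Section 2.3 and Figure 2, and protocol Section 6.1 and Figure 3, extend the sequence after OS A versus C and OS B versus C with PFS A versus C, ORR A versus C, PFS B versus C and ORR B versus C, each at two-sided 0.05 only if every earlier test is significant. In SAP Section 4.4.2 and protocol Section 6.4.2, state that any PFS or ORR p-value not reached in the sequence is descriptive. If the sponsor prefers to keep claims to OS alone, that sentence, worded to cover all PFS and ORR p-values, is the minimum.

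The cost is wording, settled before the final analysis. No data, alpha or OS power is given up. The sponsor should accept knowingly that, in this order, controlled PFS and ORR claims for the combination depend on OS success for atezolizumab monotherapy.
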